Comprehensive Geriatric Assessment for Frail Older People in Swedish Acute Care Settings (CGA-Swed): A Randomised Controlled Study

NCT02773914

2024-09-10

Study Protocol with SAP and/or ICF

Aim

The aim of the study was to evaluate the effects of the CGA for frail older people in Swedish acute hospital settings. The study addressed the following research questions:

Can the Comprehensive Geriatric Assessment for frail older people in Swedish acute hospital settings:

- 1. Maintain independence in activities of daily living, functional status, health-related quality of life and life satisfaction?
- 2. Increase satisfaction with health care?
- 3. Reduce hospital and primary health care consumption?

How feasible and acceptable are the study processes and procedures of the CGA from the perspective of care givers and older persons in Swedish settings?

Material and methods

The study was a two-armed randomised controlled trial that started with a pilot study in 2016. Ethical approval was obtained for the study, ref. no: 4,899-15, Regional Ethical Review Board in Gothenburg. Trial Registration: ClinicalTrials.gov, NCT02773914.

Data collection and participants: The study group included 155 older people who sought acute medical care at the emergency department during the period between March 2016 and December 2018. Inclusion criteria were that participants were to be ≥75 years of age, in need of acute inhospital care and screened as frail according to the FRESH-screening instrument. Exclusion criteria were not being screened as frail according to the FRESH-screening instrument, being admitted through a "fast track" for direct admission to a designated ward (for predefined diagnosis such as stroke, acute myocardial infarction and hip fracture) and having an acute severe condition requiring a higher level of care (e.g., intensive care) than the intervention ward. Baseline measures were collected by a research assistant who gathered data from the frail older patient and/or from the medical records during the hospital stay. Follow-up interviews were performed in the older person's home at 1, 6 and 12 months after hospital discharge. The follow-ups were performed using a structured questionnaire including questions about demographic data and assessments of outcome measures. The interviews lasted for approximately 1.5 h.

Intervention/control group: The intervention was the ward working according to the Comprehensive Geriatric Assessment. Key components of the CGA are multi-disciplinary teamwork, use of a personcentred approach, comprehensive assessments, treatment and rehabilitation, discharge planning and follow-up. The multi-disciplinary team consisted of a physician, registered nurse (RN), assistant nurse (AN), physiotherapist (PT) and occupational therapist (OT) as well as other team members, such as a social worker (SW) and dietician, if needed. The control group received the usual acute hospital care, i.e., care given at an ordinary medical hospital ward without a specialised multi-disciplinary team approach and without the CGA. The assessments and care provided at the control wards were based on the acute problem/symptom that the patients had and did not include the comprehensive and person-centred approach to the health and life situation of the patient inherent in a CGA.

Measurements: Dependence in daily activities was measured using the ADL-staircase assessment by combining both interviews and observations. It includes dependence in nine activities: cleaning, shopping, transportation, cooking, bathing, dressing, going to the toilet, transferring and feeding. Dependence was defined as a state in which another person is involved in the activity by giving personal or directive assistance. The sum of dependence in the nine activities of daily living is calculated, range 0−9, with a clinically significant change of ≥1 unit between baseline and follow-up.

Functional status was measured using the Timed Up and Go (TUG) test, the Berg Balance Scale, Gait Speed four-metre walking test and Grip Strength with North Coast Dynamometer. The TUG test measures the time for a person to rise from a chair, walk 3 m, turn around, walk back,

and sit down again. It measures both static and dynamic balance. In this study, we defined a change of ≥ 4 s as a clinically significant difference between baseline and follow-up, with 3.6 s considered as the minimal detectable change for TUG test measurements. For details on Berg Balance Scale, Gait Speed and Grip Strength, Cognition was measured using the Mini Mental State Examination. Self-rated was measured by the question: "In general, would you say your health is", with the response alternatives: excellent, very good, good, fair, and poor. Clinically significant difference was defined as ≥ 1 step in the response alternatives between baseline and follow-up. In addition, self-reported symptoms were measured using the Göteborg Quality of Life Instrument.

Life satisfaction was measured using the Fugl-Meyer-Lisat-11 Questionnaire which includes 11 items concerning satisfaction with: life as a whole, work, financial situation, leisure, friends and acquaintances, sexual life, functional capacity, family life, partner relationship, physical health and psychological health. Response alternatives included: very dissatisfied, dissatisfied, rather dissatisfied, rather satisfied, satisfied and very satisfied. In the analysis, the responses to each question were dichotomised into satisfied (very satisfied and satisfied) or not satisfied (rather satisfied, rather dissatisfied, dissatisfied and very dissatisfied) as was done in the validation of the questionnaire. The sum of items for which the respondent reported being satisfied were calculated, range 0–11, with a clinically significant change of ≥1 between baseline and follow-up. Satisfaction with quality of care was measured by the participant's agreement with six statements with a person-centred approach: "I feel that the care given during the hospital stay meets my needs", "I feel that the care planning meeting before discharge was valuable", "I was able to take part in the discussion of my needs in the care planning meeting", "I feel that the actions planned equal my needs", "I feel that the actions delivered equal my needs" and "I am satisfied with the hospital care". The response alternatives were agree completely, agree partly, neither agree nor disagree, disagree, and disagree completely. An answer of agree completely or agree partly were considered as satisfied. These questions were only measured once (at 1 month follow-up) and were used as the difference between intervention and control groups in the proportion of participants being satisfied for each question at follow-up as has been done previously. In this study, we used the following measurements and cut-off levels of frailty indicators: Weakness: Reduced grip strength considered to be below lowest norm range for ages 80-84, 13 kg for women and 21 kg for men for the right hand and below 10 kg for women and 18 kg for men for the left hand, using a North Coast dynamometer. Fatigue: Question from the Göteborg Quality of Life Instrument, answering "Yes" to the question "Have you suffered any general fatigue/tiredness over the last three months?"

Weight loss: Question from the Göteborg Quality of Life Instrument, answering "Yes" to the question "Have you suffered any weight loss over the last three months?"

Reduced physical activity: Taking 1–2 or less outdoor walks per week.

Impaired balance: The Berg Balance Scale, reduced balance defined as having a value of 47 or less. Reduced gait speed: Walking four metres with a gait speed of 0.6 metres/second or slower. Visual impairment: The KM chart (Konstantin Moutakis chart), impaired vision defined as having a visual acuity of 0.5 or less.

Impaired cognition: The MMSE, impaired cognition defined as having a score below 25.

Statistical analysis

A power calculation was done based on the primary outcome variable, dependence in activities of daily living (range 0–9) with an assumed difference between the intervention and control groups of one dependence (i.e., dependent in one or more activities of daily living, a clinically relevant difference of importance to the individual as well as the caregiver) and a standard deviation of 2 in both groups. To detect a difference between the intervention and control groups with a two-sided test and with a significance level of α = 0.05 and 80% power, at least 64 participants were needed in each group. To take a potential loss to follow-up into account, a total of 150 persons (75 in the control group and 75 in the intervention group) were initially planned to be included. This was later revised to allow for a higher loss to follow-up (22%) with 78 + 78, equalling a total of 156 participants.

Both descriptive and analytical statistics were used in order to compare groups and to analyse changes over time. Non-parametric statistics were used when ordinal data were analysed. Otherwise, parametric statistics were used. Besides descriptive statistics, the chi^2 and Fisher's two-tailed exact tests to test differences in the proportions among the groups were used. A value of $p \le 0.05$ (two-tailed) were considered significant. The analysis were made on the basis of the intention-to-treat principle, meaning that participants were analysed on the basis of the group to which they were initially randomised. The approach of data imputation was the replacement of missing values with a value based on the median change of deterioration between baseline and follow-up of all who participated in the follow-up.

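### Timed Up and Go is left to a ≥4 s change split or an unspecified parametric test with no baseline adjustment; either can waste power, and ANCOVA on the continuous time recovers most of it

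*Combined protocol and SAP*

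**What the plan says.** The Measurements part of Material and methods lists TUG among four functional-status measures. It sets one absolute threshold for every participant: "we defined a change of ≥ 4 s as a clinically significant difference between baseline and follow-up". Beside that threshold stands a single figure for measurement error, the same at every speed: "with 3.6 s considered as the minimal detectable change for TUG test measurements".

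The Statistical analysis section picks methods by type of scale: "Non-parametric statistics were used when ordinal data were analysed. Otherwise, parametric statistics were used". For proportions, chi-squared and "Fisher's two-tailed exact tests to test differences in the proportions among the groups were used".

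TUG time is not ordinal, so two routes are open: a parametric comparison of seconds, or a chi-squared or Fisher comparison of the share changing by at least 4 s. The plan does not say which one is the between-group test. It names no baseline covariate, transformation, relative-change rule or distribution check. TUG is assessed at baseline and follow-up, because the threshold is defined on the change between them.

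The primary outcome, and the only one with a power calculation, is ADL dependence.

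**The concern.** Functional status is part of the first research question, so TUG helps to answer a stated aim. Cutting a continuous change at 4 s discards most of the information in it. Analysing change without adjusting for baseline can also waste information already collected. In a trial of about 150 people, a real effect on mobility could then be reported as no difference.

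A fixed cut also means different things at different speeds: 4 s is 4/12 = 33% of a 12 s test but 4/60 = 7% of a 60 s test. If measurement error grew with the time taken, slow walkers would cross the line by noise more often than fast walkers. Whether it does is a separate question, which the documents do not answer.

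**Working it through.** **1. The plan's own figure.** Inputs from Statistical analysis: "an assumed difference between the intervention and control groups of one dependence", "a standard deviation of 2 in both groups", two-sided, "with a significance level of α = 0.05 and 80% power". Standardised difference = 1/2 = 0.5. Normal approximation: n = 2 × (1.96 + 0.842)² / 0.5² = 62.8, so 63. The t-test gives 63.8, so 64, with 80.1% power. The stated 64 per group reproduces, but it is for ADL. The plan gives no TUG mean, SD, effect or power, so every TUG input below is an assumption. I use 64 per arm throughout.

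**2. Hand check of the split under constant error.** Assume the SD of change is 6 s, CGA is 3 s faster, and controls do not change on average.
- Share slowing by ≥4 s, control: P(Z ≥ 4/6) = 0.252.
- Share slowing by ≥4 s, CGA: P(Z ≥ 7/6) = 0.122.
- SE of the difference = √[(0.252 × 0.748 + 0.122 × 0.878)/64] = 0.068, so z = 0.131/0.068 = 1.92.
- Power ≈ Φ(1.92 − 1.96) ≈ 49%.
- Same data, t-test on change: z = 3/(6 × √(2/64)) = 2.83; power ≈ Φ(2.83 − 1.96) ≈ 81% (about 79% by simulation).

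The cut alone costs about 30 points, with no appeal to skewness.

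**3. Simulated power (1,500 to 2,500 trials per scenario, two-sided 0.05).**
- Proportional error: lognormal times, median 25 s, log-scale correlation 0.6, CGA 20% faster.
- Constant error: median 20 s, between-person log-SD 0.3 to 0.5, SD of change 6 s, CGA 3 s faster.

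| Analysis | Proportional, log-SD 0.5 | Proportional, log-SD 0.6 | Constant error |
|---|---|---|---|
| Chi-squared on ≥4 s slowing | 62% | 47% | 49–50% |
| t-test, change in seconds | 65% | 48% | 79% |
| ANCOVA, seconds | 82% | 64% | 81–85% |
| ANCOVA, log seconds | 89% | 74% | 77–82% |

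Simulation standard error is about 1 point. Further constant-error runs gave 46–47% for the split against 80–83% for ANCOVA in seconds, and 71–81% for log ANCOVA against 81–83% in seconds.

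**4. Where the gain comes from.** At log-SD 0.5, going from the raw-change t-test to log ANCOVA gains 89 − 65 = 24 points. Baseline adjustment in seconds supplies 82 − 65 = 17 of them and the log the other 7. At log-SD 0.6 the log adds 74 − 64 = 10. Under constant error the log loses about 2 to 10 points.

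**5. Type I error.** With no treatment effect and proportional error, rejection rates for the raw-scale tests were about 4–6%.

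**6. Crossing 4 s by error alone.** P = 2 × P(Z > 4/(SEM × √2)).
- If 3.6 s is a 95% limit with constant error, SEM = 3.6/(1.96 × √2) = 1.30 s and P is about 3% at every speed (7% if it is a 90% limit).
- With an assumed 10% retest coefficient of variation, SEM = 0.10 × time and P is 2% at 12 s, 35% at 30 s and 64% at 60 s. At 25 s that assumption implies a minimal detectable change of 1.96 × √2 × 2.5 = 6.9 s, about twice the plan's 3.6 s.

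**The case against.** The strongest reply is that the documents contain nothing on the distribution of TUG times or on how error varies with speed. Their one error figure, 3.6 s, is a single constant. A reader might infer that slow walkers dominate the result and that seconds must be log-transformed. The documents support neither. Under constant error the slowest quarter supplies about 28–29% of the variation in change, close to its share of people, and the log scale loses power. Under proportional error, with log-SD 0.3 to 0.6, that share is about 48–68%. This reply stands in full: dominance by slow walkers and the 10% coefficient of variation are assumptions.

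It can also be said that TUG is not the primary outcome, that no power is claimed for it, that the effects above are assumed, and that with a small between-person spread (log-SD 0.3, 20% effect) every method has about 90% power or more. All true, and it limits the weight of the point. Nor is it certain that the ≥4 s split is the between-group test, since the plan leaves the route open.

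The reply does not rescue the split. It falls well short of the adjusted analysis under constant error as well, where skewness and proportional error play no part. Nor does it explain leaving a collected baseline value out of the model.

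**Conclusion.** The point holds as a matter of efficiency and clarity in a non-primary outcome. The plan does not name the TUG analysis, and both routes it leaves open can fall short of a baseline-adjusted analysis of the time.

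- The ≥4 s split: about 47% power against 81–83% under constant error, and 62% against 82% under proportional error with log-SD 0.5.
- The unadjusted t-test on change in seconds: 65% against 82% under proportional error. Under constant error the shortfall is small (79% against 81–85%).

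These figures rest on assumed medians, spreads, correlations and effects with 64 per arm. The ordering was the same in every scenario with a treatment effect; the size of the gap was not.

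A reader might go further and call a raw-seconds analysis invalid. The checks do not support that, since type I error stayed near 5%. The ADL sample size is not touched.

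**What to change.** In Statistical analysis, name the between-group test for TUG: ANCOVA on the continuous time at follow-up, with baseline TUG time as covariate, reporting the adjusted difference in seconds with a 95% CI. Present the ≥4 s categories by arm descriptively, without a test.

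Add a conditional rule for scale. If the pooled, blinded data show right skew and a spread that grows with the time, use log seconds with log baseline and report the ratio of geometric mean times with a 95% CI. State that proportional error is an assumption, and that the single 3.6 s figure treats error as constant.

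The cost is a few lines of SAP text, one model and one blinded distribution check, with no new data. If the log scale is used, the result is a percentage difference instead of seconds.

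### Life satisfaction and self-rated health: the change threshold is the smallest step each scale allows, and comparing arms on the proportion past it would lose power

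*Combined protocol and SAP*

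**What the plan says.** Under Measurements, the 11 LiSat items have six ordered answers. Before summing, "the responses to each question were dichotomised into satisfied (very satisfied and satisfied) or not satisfied", a cut justified "as was done in the validation of the questionnaire". The satisfied items are counted and the threshold is set: "range 0–11, with a clinically significant change of ≥1 between baseline and follow-up". For self-rated health, with five answers from excellent to poor: "Clinically significant difference was defined as ≥ 1 step in the response alternatives between baseline and follow-up". Neither threshold comes with a retest, detectable-change or anchor argument. The Timed Up and Go threshold of 4 s does: it is given "with 3.6 s considered as the minimal detectable change for TUG test measurements".

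Under Statistical analysis, the general rule is "Non-parametric statistics were used when ordinal data were analysed", with parametric methods otherwise and no test named for either. The only tests named are for proportions: "the chi^2 and Fisher's two-tailed exact tests to test differences in the proportions among the groups were used". The power calculation covers only the primary ADL outcome, as a difference in means.

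The ADL sum also uses a one-unit threshold. There the plan argues that one dependence matters to the patient and the caregiver, so the point is not extended to it.

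**The concern.** On an integer sum from 0 to 11, and on a five-level question, a rule of at least 1 separates only *any change* from *no change*. One LiSat item moving between satisfied and rather satisfied is enough to be classed as a clinically significant change. A fall on one item from rather satisfied to very dissatisfied counts as nothing. Someone already at sum 0, or at poor health, cannot be classed as worse.

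If arms are compared on the proportion crossing this line, the size of each change is discarded and one-step retest variation counts as much as a large shift. Both outcomes serve research question 1 in the Aim section, and the trial was not sized for either. A real difference could be missed on data that could have shown it.

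**Working it through.** **The plan's own figure.** ADL difference 1, SD 2, two-sided 0.05, 80% power: n = 2 × (1.960 + 0.842)² × 2² / 1² = 62.8, so 63 per arm by the normal approximation. The t-test gives 63.8, so 64, as stated. With 78 per arm and 22% loss, 78 × 0.78 = 60.8, so about 61 per arm are observed. That number is used below unless noted.

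**Inputs not in the documents.** Item switching rates, retest correlations, category splits and effect sizes are assumptions.

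**1. Chance movement.** Suppose there is no true change and each LiSat item switches independently with probability s (up s/2, down s/2). Then P(net 0) = Σₖ 11! / [k! k! (11−2k)!] × (s/2)²ᵏ × (1−s)¹¹⁻²ᵏ. At s = 0.05 this is 0.569 + 0.043 + 0.001 = 0.613, so 39% change by at least 1.

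| s | any change ≥1 | worse by ≥1 |
|---|---|---|
| 5% | 39% | 19% |
| 10% | 57% | 29% |
| 15% | 67% | 33% |

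For self-rated health, a latent-normal model with retest correlation 0.9 / 0.8 / 0.7 / 0.6 moves 36 / 47 / 54 / 60% of people by at least one level.

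**2. General cost of a cut.** Take the plan's standardised effect, 1/2 = 0.5 SD, with 64 per arm, which gives 80% power on means. If a share p₀ of controls passes the cut, p₁ = 1 − Φ(z₁₋p₀ − 0.5). At p₀ = 0.40, p₁ = 1 − Φ(0.253 − 0.5) = 0.597 and power is 61%. Over p₀ from 0.20 to 0.60, power is 55–61%, and restoring 80% takes about 100–115 per arm.

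**3. LiSat simulation.** Eleven correlated latent-normal items, true shift 0.15 SD per item, item retest correlation 0.6 / 0.8. Chi-square on the proportion worse is set against a Mann-Whitney test on the change in the 0–11 sum.

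| Retest noise | Proportion worse | Rank test, 0–11 change | Gap (points) |
|---|---|---|---|
| Independent across items | 33 / 47% | 47 / 65% | 14 / 18 |
| Independent, second item model | 38 / 51% | 48 / 64% | 10 / 13 |
| Shared across items (correlation 0.3) | 20 / 25% | 26 / 38% | 6 / 13 |

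With shared noise, retest correlation 0.6 and 75% of item answers satisfied, a check run gave 18% against 21%, a gap of 3. A working range is therefore 3 to 15 points, with 18 in the most favourable run.

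The summed six-level ratings reach 75 / 94% with independent noise but only 31 / 48% with shared noise.

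**4. Self-rated health simulation.** Five latent-normal levels, 25% at poor, shift 0.5 SD, baseline correlation 0.5 / 0.7.

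| Analysis | Power |
|---|---|
| Proportion worse by ≥1 | 42 / 57% |
| Proportion better by ≥1 | 60 / 76% |
| Rank test at follow-up, unadjusted | 76 / 75% |
| Rank analysis adjusted for baseline | 80 / 92% |

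Gaps to the adjusted analysis: 80 − 42 = 38 and 92 − 57 = 35 if worsening is counted; 80 − 60 = 20 and 92 − 76 = 16 if improvement is counted.

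**5. Null case.** With no true difference the tests rejected at 4.6–5.8%, close to nominal.

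**The case against.** The strongest objection is that no sentence assigns chi-square or Fisher to these two outcomes. The only explicit comparison of satisfied proportions is for the six care-satisfaction statements, and a rank test on the scales already falls within the non-parametric rule. This stands: a reader might infer that the plan tests the one-step categories, but the text does not say so, and the power loss is conditional on that choice. What remains is that a change cut-off has little use except to form such proportions, and that no scale-level test is named.

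A reader might also conclude that the change categories are mostly noise. That is not shown. The chance-movement figures assume no true change and independent switching at rates the documents do not give. Frail patients followed for a year after acute admission may well change. One step may also matter to a patient; the gap is that no basis is offered.

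The large gain from the six-level ratings is tempting too, but it depends on retest noise being independent across items and shrinks sharply otherwise. The yes/no item scoring has a stated rationale in the questionnaire's validation and need not be overturned. That rationale supports the item cut, not a change threshold of 1.

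Finally, the upper end of the self-rated health gap combines three things: the cut, the weaker direction of change, and the absence of baseline adjustment. This is correct, and the range is given with that caveat.

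**Conclusion.** The point holds in conditional form. Both thresholds equal the smallest possible step and lack the measurement-error basis given for Timed Up and Go. If arms are compared on the proportion changing by at least 1, the loss is roughly 3 to 15 points of power for LiSat, mainly according to whether retest noise is shared across items. For self-rated health it is roughly 15 to 40 points, part of it due to baseline adjustment and to the direction counted. The sizes rest on assumed inputs; the ordering held in every scenario run. Chance switching affects both arms alike, so it dilutes a difference and does not create one. These are not the primary outcome, so this is a worthwhile, low-cost improvement and not a threat to the main result.

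**What to change.** State in Statistical analysis that the between-arm comparison for both outcomes is a rank-based or ordinal analysis of the full scale, adjusted for the baseline value. For LiSat this is the 0–11 sum with the validated item scoring kept; for health, the five levels. Report improved, unchanged and worse by arm as description only, and do not call a one-step change clinically significant unless a reliability or anchor basis is cited. The summed six-level LiSat ratings may be added as an optional sensitivity analysis.

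The cost is a few sentences and a few lines of code on data already collected. There are two downsides. A shift or odds ratio is less immediate than a percentage, though the percentages stay in a table. And because data collection is over, any analysis that was not pre-specified must be labelled post hoc or supplementary, so that it is not read as a switch made after seeing the results.

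### The plan does not say whether Berg balance, gait speed, grip strength and MMSE are compared between arms as scores or at the frailty cut-offs, and it states no baseline adjustment

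*Combined protocol and SAP*

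**What the plan says.** Under Aim, research question 1 asks whether the intervention can "Maintain independence in activities of daily living, functional status, health-related quality of life and life satisfaction". Under Measurements, "Functional status was measured using the Timed Up and Go (TUG) test, the Berg Balance Scale, Gait Speed four-metre walking test and Grip Strength". Cognition is measured with the MMSE.

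The same section defines a clinically significant change from baseline for ADL dependence (1 unit), TUG (4 s), self-rated health (1 step) and life satisfaction (1 item). It defines none for Berg, gait speed, grip strength or MMSE. A sentence that begins by referring to details of Berg, gait speed and grip strength runs straight into the MMSE without giving any.

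The numerical rules that do exist for these four come in the list at the end of Measurements, introduced with "we used the following measurements and cut-off levels of frailty indicators: Weakness: Reduced grip strength considered to be below lowest norm range for ages 80-84". The list continues with Berg ("The Berg Balance Scale, reduced balance defined as having a value of 47 or less"), gait speed ("Walking four metres with a gait speed of 0.6 metres/second or slower") and the MMSE ("impaired cognition defined as having a score below 25").

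Under Statistical analysis, the general rule is non-parametric methods for ordinal data and parametric methods otherwise. The only tests named are these: "the chi^2 and Fisher's two-tailed exact tests to test differences in the proportions among the groups were used". No model and no covariate is mentioned.

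**The concern.** A reader who tries to carry out the analysis of balance, gait speed, grip strength or cognition finds one concrete number per measure (for grip, one per sex and hand), each a cut-off, and one concrete family of tests, for proportions. Nothing states the outcome form, the test or the role of the baseline value. Both a comparison of scores and a comparison of percentages impaired could be reported as planned.

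The choice matters because the question is about maintaining function. At a fixed cut, a fall in Berg from 40 to 15, or in gait speed from 0.5 to 0.2 m/s, counts as no change, while a one-point move from 48 to 47 counts as new impairment. Everyone enrolled is 75 or older, in need of acute hospital care and screened as frail, so a sizeable share may be below a cut at entry. The documents do not give that share.

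The silence on baseline is a separate loss. Baseline data are collected, and even a full-scale comparison wastes information if it ignores them.

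**Working it through.** **Inputs from the Statistical analysis section.** ADL difference 1, SD 2, 80% power, 64 per group; the level and sidedness are given in "To detect a difference between the intervention and control groups with a two-sided test and with a significance level of α = 0.05".

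**Assumptions, not in the documents for these four measures.** Standardised difference d = 1/2 = 0.5, borrowed from ADL; normal scores; 64 per arm analysed; 50-90% of controls below the cut at follow-up; baseline-to-follow-up correlation 0.5 or 0.7.

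**Step 1: the plan's own figure.** A two-sample t-test with d = 0.5 needs 63.8, so 64 per group, which reproduces the plan. Power at 64 per arm is 80.1%. This is the reference for an unadjusted full-scale comparison of follow-up scores.

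**Step 2: the same difference tested at a cut.** If a proportion p of controls is below the cut, the intervention proportion is Φ(Φ⁻¹(p) − 0.5). Chi-square power (no continuity correction) and Fisher power are by exact enumeration with 64 per arm. The last column uses the normal-approximation formula for two proportions.

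| Controls below cut | Intervention below cut | Chi-square power | Loss against 80.1% | Fisher power | n per arm for 80% (chi-square) |
|---|---|---|---|---|---|
| 50% | 30.9% | 61.4% | 18.7 points | 54.5% | 102 |
| 70% | 51.0% | 61.3% | 18.8 points | 54.4% | 103 |
| 80% | 63.4% | 56.1% | 24.0 points | 47.5% | 115 |
| 90% | 78.3% | 44.0% | 36.1 points | 35.6% | 152 |

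The normal-approximation formula gives chi-square powers of 59.9, 59.7, 55.2 and 44.2%, which leads to the same conclusion. With Fisher's test the loss runs from about 26 to 45 points.

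**Step 3: full scale with baseline adjustment.** ANCOVA reduces the residual SD by √(1 − ρ²), so the effective difference is 0.5/√(1 − ρ²).

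- ρ = 0.5: 0.5/0.866 = 0.577, power 90.0%.
- ρ = 0.7: 0.5/0.714 = 0.700, power 97.6%.

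**Step 4: comparing change scores.** The plan mentions analysing changes over time. The SD of a change is √(2(1 − ρ)) in units of the score SD. At ρ = 0.5 this is 1, so power stays at about 80%. At ρ = 0.7 it is 0.775, so the effective difference is 0.5/0.775 = 0.645 and power is about Φ(0.645 × √32 − 1.96) = Φ(1.69), or 95%. ANCOVA does better in both cases.

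**The case against.** The strongest objection is that the plan never says these outcomes are tested as impaired or not impaired. The cut-offs are introduced as frailty indicators and share a list with fatigue, weight loss, outdoor walks and vision, which reads as a definition of frailty and not as outcome scoring. Where the plan does dichotomise for analysis, for life satisfaction items and satisfaction with care, it says so. The general rule leaves room to analyse gait speed and grip parametrically and Berg and MMSE by ranks. Imputation from a median change also sits more naturally with retained scores. The incomplete sentence on Berg, gait speed and grip may have lost a pointer to further detail, so it is not evidence either way.

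All of this stands. A reader might infer that the between-arm tests are run at the cut-offs and that the trial therefore loses 19 to 36 points of power; the documents do not support that as a statement of fact. Nor do they support saying that a real difference would probably be missed. Under the assumptions above, chi-square power stays above one half with 50-80% of controls below the cut. Counting only newly impaired participants would be a further analysis that the plan does not describe, so no figure for it is used here. Cognition is not named in research question 1, so the MMSE is included only because it has the same gap.

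What the objection does not remove is the gap itself. The general rule does not tie these four measures to their full scale, just as the line on proportions does not tie them to the cut-offs. No passage gives their outcome form, test or baseline adjustment.

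**Conclusion.** The point holds as a specification gap in four secondary outcomes, three of which make up most of the functional-status part of research question 1. It is worth correcting, with medium confidence. It does not touch the primary outcome or its sample size of 64 per group, which reproduces.

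The size is conditional. If the cut-offs were used for testing, chi-square power would be about 61% to 44% instead of 80%, and decline below a cut would be invisible. If unadjusted follow-up scores were used, power would be 80% where baseline-adjusted analysis offers about 90% to 98%. Both rest on a 0.5 SD difference borrowed from ADL, normal scores and 64 analysed per arm. The first also depends on the assumed share below the cut, and the second on the assumed correlation.

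**What to change.** State that the between-arm comparison of Berg score, gait speed (m/s), grip strength (kg) and MMSE score uses the full measured value at follow-up, by ANCOVA with the participant's own baseline value as covariate. For Berg and MMSE, provide a rank-based or proportional-odds version if scores bunch at a limit of the scale. Say explicitly that the cut-offs serve to describe frailty and, at follow-up, to give descriptive proportions only.

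The cost is analysis wording and a re-run on data already collected, with no new measurements or participants. The plan reports baseline collection in general without listing the measures, so the sponsor should confirm that all four were taken at baseline. Mean differences are less immediate to clinicians than a percentage impaired, but that percentage can still be shown alongside.
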